10.0 Data and Specimen Banking

10.1 Participant data will be collected using the Northwestern-based REDCap survey platform and Northwestern's Sharepoint (for EHR extraction data) and all data will be stored under an ID number. Upon completion of all study activities, a final de-identified dataset will be created. This dataset will be stored indefinitely on the GIM server for secondary analyses. Only authorized personnel will have access to the dataset. Data will be stored on Northwestern encrypted servers and access will be granted through the PI.

11.0 Data and Specimen Management

11.1 Analysis Plan – Aim 1

The proposed trial uses stratified randomization with random block size to achieve group comparability and balance. Stratified by clinic, and provider type (full time, part-time, resident) randomization occurs at the provider level, where patients are randomized to the same group as their provider. Each provider (approximately 201 across the 2 sites, 100 per site) will be randomized to one of three arms resulting in approximately 67 physicians per arm. We will assume 4 patients per provider, and conservatively anticipate at least 80% retention for follow-up at six months. This will result in 900 participants recruited to the study with an anticipated minimum of 720 (240 patients per arm, 3 per physician) available after 6 months, contributing to primary data analysis.

To ensure adequate balance across treatment arms, baseline outcomes and potential confounders including socio-demographic characteristics, comorbidities, regimen complexity (i.e., # of medications, total pills taken daily), health literacy, and language will be compared across arms using descriptive statistics. Additionally, these variables will be examined one-at-a-time for associations with effectiveness outcomes, and those variables found to have significant associations with outcome(s) will be considered potential covariates in the generalized linear mixed models (GLMMs) used for formal analyses as described below. Backward stepwise model building approaches will be used to determine final, parsimonious model(s) for study outcome(s).

Prescription medication adherence at 6 months is the primary outcome of interest for Aim 1, with treatment knowledge, demonstrated proper Rx use, and regimen consolidation outcomes relevant to hypotheses of secondary interest. For each outcome, we will use generalized linear mixed-effects models (GLMMs) to test for the effects of EHR and SMS text reminders, specifying the proper link functions

Regimen Education and Messaging in Diabetes (REMinD)

based on the distribution of the outcome variable. The GLMMs will include random provider effects and fixed binary variables for SMS text reminder and EHR to denote the intervention groups and the usual care group (H1-4). We will include a fixed indicator variable for clinic in the GLMMs and any potential confounding covariates as noted above. Analyses will be performed using PROC GLMMIX in SAS (v.9.3) and lme4 package in R. Since understanding and adherence will be assessed for each medication, 2-level GLMM will be used with medications nested in participants. We will first test for differences in the outcomes between the EHR group and usual care (H1-3), followed by comparisons between EHR+SMS vs. usual care, and EHR vs. EHR+SMS to determine additional benefits of SMS texting (H4) by constructing contrasts.

Aim 2

We will include both literacy-by-arm and language-by-arm fixed interaction terms in the above GLMMs for all outcomes. We will use the corresponding model type III tests for fixed effects to determine significance of terms, and construct appropriate contrasts for pairwise comparisons for each literacy level and each language.

Aim 3

We will determine the extent to which the interventions were implemented as planned (a process evaluation) across each site and for all three study arms, in order to optimize the intervention for future dissemination opportunities.

Mixed methods will be employed using a convergent parallel design to obtain data on intervention implementation.

Quantitative and qualitative findings will be merged to answer 1) whether either intervention was implemented as planned, 2) from a user-perspective, do interventions require modification and how. In this approach, both analyses are conducted separately and merged for side-by-side data comparisons. For quantitative data (patient report, EHR data), frequencies will be generated to determine outcomes related to receipt of materials, perceived helpfulness of materials, CAHPS and PACIC. For CAHPS and PACIC data, similar GLMM models as described in Aim 1 analyses will be performed, with intervention arm as the primary independent variable. For qualitative data, we will review and explore the transcribed patient interviews and clinic staff discussions using content and ethnographic analysis. Predetermined categories will organize feedback from all users: patient, provider, clinic/health system. Within each of these broad categories we will use a predetermined coding approach to quantify the frequency of two subcategories: facilitating factors, and impeding factors (see Figure 8). An additional layer within impeding factors would be whether factors are modifiable or not, and under facilitating factors, if they are replicable. Field notes and quantitative findings will be integrated in this model. Transcribed interviews and field notes will be examined by the study team independently to see if modifications to the categories are needed.

Aim 4:

We will directly measure and assess the provider perspective costs of developing and running UMS interventions, alone and in combination. Incremental cost of

Regimen Education and Messaging in Diabetes (REMinD)

interventions will be estimated relative to usual care from the perspective of NMHC, NM Regional Medical Group, and MSMC practices implementing these processes and tools. First, we will document the initial costs associated with programming the EHR tools at a new site, following the code and standard operating manual guidance from Aim 3. The primary costs of running these UMS technologies in the EHR arm involves the limited expenses around printing the EHR tools (printer ink, paper, staff time) as a result of generating new Rx information with after-visit summaries. SMS monthly costs will be easily documented from EZText invoices as well as usage. However, we will include estimates for programming maintenance for Epic EHR, and will test the sensitivity of results to changes in the maintenance requirements in terms of programmer hours, calculated per site. We also will separately track development costs for software and other programming requirements based on programmer hours. Staff/programmer costs will be measured using tracked time spent on the intervention and wage estimates. We will test the sensitivity of operational costs to different assumptions about the potential use of variable staff using different salaries but assuming the same proficiency in terms of time required. Further, we will assess the sensitivity of estimates to different proficiency levels that could arise from learning by doing.

Exploratory Analyses. We will repeat all GLMM analyses described for Aim 1 to explore whether differences in interventions vary by relevant covariates representing patient and regimen characteristics known to impact outcomes, specifically adherence. Interaction terms will be included in models accordingly. As adherence has its many measurement challenges, experts recommend triangulating with multiple measures. We will compare results across each adherence measure (ASK-12, 24-hour recall, pill count) and create a general estimate of adherence via single factor score using maximum likelihood estimation. Exploratory analyses will examine HbA1c and blood pressure from baseline to 6 months, although power may be limited. Additionally, we will construct marginal models for all primary and secondary outcomes using generalized estimating equations (GEE) in a process similar to those described for the GLMMs. The purpose is to obtain population-averaged estimates of any differences in outcomes across arms vs. estimates at participant level.

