The 3 month interview will take place over the phone and patients will be asked additional questions about how they take their medicines, their diabetes as well as gather information about receipt of UMS tools, filled prescriptions and text reminders.

The 6 month follow-up interview will take place in-person or over the phone and will gather information about receipt of UMS tools, filled prescriptions, text reminders, self-report of physician medication-related communication at recent encounter as well as complete 3 additional blood pressure readings, and the pill count. The blood pressure reading will be excluded if the interview must be completed over the phone. If the interview is completed over the phone, the same pill count protocol for baseline will be followed for 6 month. For patients consented before May 19, 2020, a brief

Regimen Education and Messaging in Diabetes (REMinD)

script will be read informing patients of the change in the consent in regards to the pill count. The RC will ask the participant to provide verbal consent to allow the study team to take a screen shot/photograph of the patient's pills during a video call in order for the RC to count the pills after the interview. The patient will be notified that no PHI will be captured in the photograph.

At the 6 month interview, in addition to the activities that will take place during the 3 month interview, patients from the intervention arm will also be asked additional, semi-structured questions to explore 1) personal challenges with regimen adherence, 2) perceived value of the EHR and SMS tools, 3) unmet needs and acceptability of other tools and approaches to support medication use.

Clinic Staff Feedback

Among consenting physicians, we will ask physicians to complete a brief survey about their experience using the tools. (See Provider feedback survey)

Medical Record Extraction:

Additional chart data will be abstracted via an additional EDW report including patient medications, chronic conditions, COVID-19 diagnosis an/or results of antibody test, and healthcare utilization (ED, hospitalization, primary care appointments) as well as hypertension, diabetes and cholesterol clinical values. Furthermore, we will extract whether patients received prescription orders in UMS format (with after-visit summaries) and the corresponding. We will also note when (days post visit) the Medication reconciliation sheet was incorporated into the EHR.

Field Notes:

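### The primary model uses 6-month adherence alone and states no missing-data method, so up to 20% of patients leave the arm contrasts, which can bias them if the dropout–adherence link differs by arm

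*Combined protocol and SAP*

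**What the plan says.** Section 11.1 (Aim 1): "Prescription medication adherence at 6 months is the primary outcome of interest for Aim 1". The planners "conservatively anticipate at least 80% retention for follow-up at six months" and project a minimum of 720 of 900 patients "available after 6 months, contributing to primary data analysis".

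On the model: "The GLMMs will include random provider effects and fixed binary variables for SMS text reminder and EHR to denote the intervention groups". A fixed clinic indicator is added. Covariates, including baseline outcomes, enter only if they show an association with the outcome and survive backward selection. Because adherence is assessed per medication, a "2-level GLMM will be used with medications nested in participants". Visit is neither a model term nor a level.

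Section 9.9 describes follow-up at 3 and 6 months: "The 3 month interview will take place over the phone and patients will be asked additional questions about how they take their medicines". Its measures table schedules ASK-12 and 24-hour recall at 0, 3 and 6 months, and pill count at 0 and 6 months only. The plan does not say which measure carries the primary analysis; under Exploratory Analyses it states: "We will compare results across each adherence measure (ASK-12, 24-hour recall, pill count)".

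Section 13.2 says that data gathered before a withdrawal will be used, without naming an analysis. No missing-data method, missingness assumption or dropout sensitivity analysis is stated. The exploratory GEE models follow a process similar to the GLMMs and add none.

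**The concern.** A model of the 6-month value alone silently omits anyone without that value. Up to a fifth of patients may be omitted, although their baseline adherence, and for some their 3-month adherence, will have been recorded.

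Patients who take their medicines poorly may also be the ones who stop answering calls. The arms differ in what patients experience: orientation and tools in the intervention arms, texts in one of them, and extra semi-structured questions for intervention patients at the 6-month interview. If these change who is lost, the patients left at 6 months are no longer comparable between arms, and the error falls on the primary contrasts. Baseline adherence would give partial protection, but covariate selection does not guarantee that it stays in the model.

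**Working it through.** **Inputs.** From the documents: 900 enrolled, 80% retention, three arms (11.1); 45% adherent in usual care, a 14-point difference, hence 59%, and 1.67% alpha per comparison (11.2). Assumed, because the documents give nothing: how loss relates to adherence, and a latent correlation of 0.5 to 0.7 between adherence measures. Provider clustering is ignored.

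**1. The plan's figure.** 900 × 0.80 = 720, or 240 per arm. Missing: 900 − 720 = 180, or 60 per arm. The stated figure reproduces.

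**2. When loss biases the contrast.** Let p be true adherence, and rA and rN the retention of adherent and non-adherent patients. The rate seen is p·rA / (p·rA + (1 − p)·rN), so the odds seen are the true odds × rA/rN.

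- *Same link in both arms.* rA/rN cancels and the odds ratio stays at (0.59/0.41)/(0.45/0.55) = 1.76. With rA = 0.896 and rN = 0.696, the rates seen are 64.9% and 51.3%, a difference of 13.6 points against a true 14.0.
- *Link in the intervention arm only, 20-point retention gap.* 0.59 × 0.882/0.80 = 65.0%, so 14 points is seen as 20.0. With a 5-point gap it is 15.5.
- *Link in usual care only, 20-point gap.* 0.45 × 0.91/0.80 = 51.2%, so 14 points is seen as 7.8. With a 5-point gap it is 12.5.
- *No true effect (45% in both arms), link in one arm only.* The false difference is 1.5 to 6.2 points. With SE = √(2 × 0.45 × 0.55/240) = 0.045, rejection at a nominal 1.67% (taken as two-sided) rises to about 2.3% to 15%.

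In this step loss depends on 6-month adherence itself, which imputation from earlier data cannot fully correct.

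**3. Loss that depends on 3-month adherence, intervention arm only.** Suppose 37% of patients non-adherent at 3 months are lost and 8% of adherent ones. With 59% adherent at 3 months, loss is 0.41 × 0.37 + 0.59 × 0.08 = 19.9%, as planned. For correlated normal variables cut at 59%, 6-month adherence is 72.6% in those adherent at 3 months and 39.5% in the others (correlation 0.5), or 79.1% and 30.0% (correlation 0.7).

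- Correlation 0.5: (0.59 × 0.92 × 0.726 + 0.41 × 0.63 × 0.395)/0.801 = 61.9%, a bias of +2.9 points.
- Correlation 0.7: (0.59 × 0.92 × 0.791 + 0.41 × 0.63 × 0.300)/0.801 = 63.3%, a bias of +4.3 points.
- Weaker links, unadjusted: 30% vs 13% lost gives +1.7 to +2.5; 25% vs 16.5% gives about +0.9 to +1.2.
- The strong link placed in usual care only: about −3 to −5.

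**4. With baseline adherence in the model.** In simulations with 1,000,000 patients per arm, adjusting completers for baseline pill count and recall cut the strong-link bias to about +1.5 to +1.7 points. Half that link left about 0.7 to 0.8.

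**5. What 3-month data recover.** When every dropout has a 3-month value and loss depends only on it, multiple imputation left 0.2 points of bias or less. If half the dropouts lack that value, about 0.7 points remain. If all lack it, the result equals the baseline-adjusted completer result.

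**6. Precision under random loss.** Approximate effective n per arm is 240 + 60·f·ρ², where f is the share of dropouts with a 3-month value and ρ its correlation with the 6-month value. For f from 0.5 to 1 and ρ from 0.3 to 0.7 this is 243 to 269, so the SE falls by 1 − √(240/243) = 0.6% to 1 − √(240/269) = 5.5%. Simulation gave 2% to 4%.

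**The case against.** The 720 is a retention projection, not a defined analysis set, and Section 13.2 says data before withdrawal will be used. Both points stand. A reader might infer that the plan adopts a completers-only set and excludes 3-month data; the documents do not say so. But Section 13.2 names no analysis, and a model with no visit term gives 3-month outcomes no stated place.

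A reader might also infer that loss of non-adherent patients by itself biases the result. It does not: step 2 shows that an equal link leaves the odds ratio unchanged and moves the difference by less than half a point.

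The case for differential loss is thin. Texts run for 7 days after baseline and again after new prescriptions or significant regimen changes, and patients can cancel them. Interview timing and retention mailings are the same in all arms, and the 6-month interview may be by phone. Baseline adherence, if strongly predictive, would probably survive selection, so the adjusted figures are the fairer guide. All of this limits the likely size of the bias.

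Finally, pill count has no 3-month value. That is true, but 3-month ASK-12 and recall can still help predict a missing 6-month pill count.

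**Conclusion.** The point holds as a risk with an inexpensive remedy. As written, patients without a 6-month value, up to 180 of 900, do not inform the primary contrasts, and their earlier adherence data go unused. Bias of any consequence needs a dropout–adherence link that differs by arm, and it can go either way.

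Under a strong assumed link in the intervention arm only, it is about 3 to 4 points on a 14-point effect unadjusted and about 1.5 points with baseline adherence in the model. Half that link leaves about 0.7 to 0.8 points adjusted. A link equal across arms leaves almost none.

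These sizes rest on assumed loss patterns and correlations. The documents contain no dropout figures by arm or by adherence, so they do not support saying that the contrasts will be biased. The remedy works best for patients who reach month 3 and are lost for reasons their recorded data explain.

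**What to change.** In Section 11.1:

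- Define the primary analysis population as all enrolled patients, by their provider's arm, and state which adherence measure is primary, since the method depends on it.
- For ASK-12 and 24-hour recall, fit one longitudinal GLMM to the 3- and 6-month values. Include arm-by-time terms, the baseline value as a covariate that is always kept, and provider and patient random effects. Take the 6-month contrasts as primary.
- For pill count, multiply impute the missing 6-month patient-level value within arm, from baseline pill count and from baseline and 3-month ASK-12 and recall, respecting provider clustering. A patient-level value fits Section 11.2, which works with the proportion of patients adherent.
- Keep the completer GLMM as a sensitivity analysis, and add one for dropout that is not missing at random.

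The cost is SAP wording and extra programming, with no new data. The analysis would rely on missing-at-random given baseline and 3-month adherence. A patient with neither follow-up value adds nothing to the longitudinal model, so the gain is limited for early losses. The precision gain under random loss is small, about 2% to 4% in SE.

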1.0 Objectives

We will leverage increasingly available technologies to impart a Universal Medication Schedule (UMS) in primary care to help patients living with diabetes safely use and adhere to complex drug regimens. We will conduct a 3-arm, multi-site trial to:

1.1 Specific Aims:

1. Test the effectiveness of the UMS, and UMS + SMS text reminder strategies compared to usual care.
2. Determine if the effects of these UMS strategies vary by patients' literacy skills and language.
3. Using mixed methods, Evaluate the fidelity of the two strategies and explore patient, staff, physician, and health system factors influencing the interventions.
4. Assess the costs required to deliver either intervention from a health system perspective.

1.2 Hypotheses:

1. Compared to usual care, patients receiving the UMS or UMS+SMS text reminder strategies will demonstrate a better understanding of how to safely dose their Rx regimen
2. Compared to usual care, patients receiving the UMS or UMS+SMS text reminder strategies will when possible, take their Rx regimen fewer times per day
3. Compared to usual care, patients receiving the UMS or UMS+SMS text reminder strategies will have greater adherence to their Rx regimen
4. Compared to the UMS only arm, patients receiving the UMS+SMS strategy will have greater adherence to their Rx regimen.
5. The intervention effects will be greater among those with limited literacy and English proficiency.

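### Adjustment covariates are chosen from outcome data by a stepwise rule with no thresholds, and nothing keeps the literacy and language main effects that the Aim 2 interactions need

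*Combined protocol and SAP*

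**What the plan says.** Section 11.1 (Aim 1) first describes baseline outcomes, sociodemographics, comorbidities, regimen complexity, health literacy and language by arm. It then tests each of them singly against the effectiveness outcomes, and "those variables found to have significant associations with outcome(s) will be considered potential covariates in the generalized linear mixed models (GLMMs". The last step is selection: "Backward stepwise model building approaches will be used to determine final, parsimonious model(s) for study outcome(s". No p-value or other criterion is given for the screen or for removal.

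The terms that are fixed come next: "The GLMMs will include random provider effects and fixed binary variables for SMS text reminder and EHR to denote the intervention groups", and "We will include a fixed indicator variable for clinic in the GLMMs and any potential confounding covariates as noted above". For outcomes measured per drug, a "2-level GLMM will be used with medications nested in participants".

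For Aim 2: "We will include both literacy-by-arm and language-by-arm fixed interaction terms in the above GLMMs for all outcomes", and "We will use the corresponding model type III tests for fixed effects to determine significance of terms". The plan does not say whether a main effect removed in the Aim 1 selection returns. The hypothesis under test (section 1.2, number 5) is that "The intervention effects will be greater among those with limited literacy and English proficiency".

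On strata, section 11.1 names clinic and a three-level provider type. Section 9.2.1 names workload and health center, in four groups. Section 12.1 gives the DSMB approval of the analysis plan.

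**The concern.** The covariate set depends on the trial's own outcome data and on thresholds still to be chosen, so two analysts following the text could fit different primary models. Three things are left unprotected:

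- **Provider type.** It is a stratifier in section 11.1 but is neither a model term nor a named candidate.
- **Baseline outcome.** It is only a candidate, so it may be in the model for one outcome and absent for another.
- **Literacy and language main effects.** Both are in the pool that can be pruned, yet Aim 2 adds their interactions to the pruned models. An interaction without its main effect tests a different hypothesis from the one in section 1.2.

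At stake are the reproducibility of the primary model and its alignment with the randomisation, and the validity of the Aim 2 tests.

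**Working it through.** The plan gives no figure for covariate selection or for Aim 2 power. Its one power statement (sections 11.2 and 11.3) concerns pairwise arm comparisons and is not used here.

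**1. Status of each term**

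| Term | Role | Status in the model |
|---|---|---|
| EHR, SMS | arms | fixed |
| Provider | randomised unit | random effect |
| Clinic | stratifier | fixed |
| Provider type | stratifier (11.1) | not mentioned |
| Baseline outcome | prognostic | candidate, can be dropped |
| Literacy, language | Aim 2 modifiers | candidates, can be dropped |

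**2. Primary contrast.** Inputs from the plan: 240 patients per arm and a pairwise level of 1.67%. Assumptions: 12 candidate covariates, binary outcome, linear model, no clustering, 10,000 null trials. The simulation standard error is √(0.0167 × 0.9833 / 10,000) = 0.13 points.

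- All covariates pre-specified: type I error 1.67%.
- Screening plus backward selection with the cut-off fixed in advance: 1.73% (p<0.05), 1.68% (p<0.10), 1.71% (p<0.20).
- Smallest p-value over those three models, the unadjusted model and the full model: 2.36%.

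Omitting provider type: with 3 patients per provider and the plan's upper ICC of 0.01, the design effect is 1 + (3 − 1) × 0.01 = 1.02. Its square root is 1.010, so at most about 1% of the standard error is at issue.

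**3. What dropping a main effect does.** Let L mark limited literacy. Code EHR = 1 in both active arms and SMS = 1 only in the combined arm. The linear predictor is

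β0 + β1·EHR + β2·SMS + γ·L + δ1·EHR·L + δ2·SMS·L.

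The literacy gap is γ in usual care, γ + δ1 with EHR, and γ + δ1 + δ2 with EHR+SMS. The model has 6 parameters for 3 arms × 2 literacy levels. Dropping γ with numeric 0/1 terms leaves 5 parameters and forces the usual-care gap to zero. δ1 then estimates the gap inside the EHR arm, which is near zero if EHR closes the gap.

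If EHR and SMS are entered as factors, the interactions still supply three literacy columns. The rank stays at 6 and the usual-care gap is still estimated. The literacy terms then test whether a gap exists in any arm, not whether gaps differ.

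**4. When selection would drop literacy.** With equal arms, a 15-point usual-care gap closed in both active arms pools to (15 + 0 + 0)/3 = 5 points. If it is only halved, it pools to (15 + 7.5 + 7.5)/3 = 10 points and is much easier to detect.

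**5. Simulated size.** Plan structure: 67 providers and 240 patients per arm (39 × 4 + 28 × 3 = 240), 5 drugs per patient (the eligibility minimum), ICC 0.01, and mean adherence of 45% in usual care and 59% in the active arms. Assumptions: limited-literacy prevalence 25% or 50%, within-patient latent correlation 0.3 or 0.6, p<0.05 for screen and retention, numeric EHR and SMS. The test is a 2-df likelihood-ratio test at 5%, with 500 trials per setting. The order is (prevalence, correlation) = (0.25, 0.3), (0.25, 0.6), (0.5, 0.3), (0.5, 0.6).

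| Assumed pattern | Rejection %, main effect always kept | Rejection %, kept only if selected |
|---|---|---|
| 15-point gap, closed | 70.2, 50.6, 80.4, 65.0 | 35.6, 17.4, 47.0, 27.0 |
| 10-point gap, closed | 35.6, 27.2, 49.8, 33.6 | 11.6, 6.6, 15.8, 10.0 |
| 15-point gap, halved (0.25, 0.6 only) | 18.6 | 16.0 |
| Constant 5-point gap, no effect modification | 4.4, 5.4, 7.4, 7.8 | 6.6, 7.2, 8.0, 8.2 |

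In the 15-point closed pattern, trials in which literacy was dropped rejected in only 7.3, 3.4, 5.3 and 4.3%. The mean EHR-by-literacy log-odds was 0.77–1.09 with the main effect and about 0 without it. The simulation standard error is 1–2 points overall and up to about 3 in the dropped trials.

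**6. Sensitivity.**

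- *Cut-off.* A simpler patient-mean linear model (no provider effect, 1,500 trials per setting) gives 50–82% with the main effect kept. Kept only if selected, it gives 18–50% at p<0.05 and 31–68% at p<0.20.
- *Halved gap.* In the same model, over all four settings at p<0.05, power is 15–28% against 13–28%, with literacy retained in 87–99% of trials.
- *Coding.* With arm as one three-level class variable, trials where literacy was dropped reject in 52–79% at 15 points, on a 3-df test.

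**7. Contrasts by literacy level.** At 25% limited literacy and a 15-point gap, usual care is 45 − 0.75 × 15 = 33.75% (limited) and 48.75% (adequate). Against 59% the effects are 25.25 and 10.25 points. With the usual-care gap forced to zero, both contrasts read about 59 − 45 = 14 points.

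**The case against.** The power loss is conditional. Selection must drop literacy, the analyst must fit interactions without main effects, EHR and SMS must be numeric, and the gap must be nearly closed under a strict cut-off. The plan states none of these. Many analysts would keep main effects by convention, and the planned contrasts at each literacy level suggest that literacy would be in the model. Section 2.1 calls the evidence linking literacy to non-adherence inconclusive, so a 15-point gap is an assumption. Section 11.2 bases the sample size on pairwise arm comparisons, and no Aim 2 power is claimed. The candidate list is also open-ended, so provider type is unnamed rather than excluded. All of this stands and limits the size of the point. It does not supply the missing rule, and neither does DSMB approval of a plan that leaves the rule open.

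A reader might infer that stepwise selection inflates the primary type I error. The check does not support that for a rule fixed in advance. The 2.36% arises only from picking the best of five models, which the plan does not propose.

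Forcing in the baseline outcome also carries a risk. Tools are switched on by provider (section 9.2.1), patients can receive them before being approached (section 28.1, non-consenting patients), and the section 9.9 table records receipt of UMS materials at month 0. Baseline adherence may therefore already reflect exposure, so an analysis without it is needed.

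**Conclusion.** The point holds as a gap in specification. Covariates are chosen from outcome data with no stated rule, a stratifier is left out of the model, and the Aim 2 main effects are not protected.

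- **Primary contrasts:** no material type I error or precision harm is shown if the rule is fixed in advance. The gain is a reproducible model aligned with the randomisation.
- **Aim 2:** if a main effect is dropped and not restored, the interaction test no longer isolates effect modification, whatever the coding. With numeric coding, p<0.05 selection and a 15-point gap fully closed in both active arms, power falls from 51–80% to 17–47%.

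The documents do not support the stronger inference that Aim 2 will lose this power. Gap sizes, correlations and cut-offs are assumptions. The simulation covers literacy only, with one candidate covariate, and uses likelihood-ratio rather than type III F tests. Language has the same structure but was not simulated.

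**What to change.** Replace the screening and stepwise sentences in section 11.1 with a fixed list for the primary and secondary models:

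- arm (EHR, SMS) and clinic;
- provider type as actually used to stratify;
- the month 0 value of the same outcome, summarised per patient so that drugs started after baseline are not lost;
- literacy and language main effects;
- random provider effects, with medications nested in participants.

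Then:

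1. Define the Aim 2 model as this model plus the literacy-by-arm and language-by-arm terms, with both main effects always kept, and state the coding of EHR and SMS.
2. Require a sensitivity analysis without the baseline term.
3. Reconcile the strata first. Section 9.2.1 gives four groups, but 2 workload levels × 3 health centers make 6, and section 11.1 has three provider types.
4. Tie the baseline term to month 0 rather than to a month 6 counterpart, because the section 9.9 table lists treatment knowledge only at months 0 and 3.
5. Use the same list in the GEE models, label any stepwise model exploratory, and lock the list when the DSMB approves the analysis plan.

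The cost is wording and a few degrees of freedom; no new data collection is needed. Which adherence and literacy instruments to use is a separate matter.
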